## **PROTOCOL TITLE: Testing mHealth Delivery of Cognitive Behavioral Therapy for Insomnia to Breast Cancer Survivors**

Additional analyses will describe mean changes within groups and test change using paired t-tests. We will also analyze whether we met the clinically relevant target for success of sub-threshold or better scores ( $\leq 14$ ) among  $>80\%$  of the intervention participants. Group differences at post-intervention will be assessed by logistic regression, controlling for baseline ISI score.

### **Analysis of the Secondary Endpoint(s)**

We also plan to calculate differences between study arms for the following CSD metrics: sleep efficiency, wake after sleep onset, sleep onset latency, total sleep time and sleep quality. We will calculate descriptive statistics (means and standard deviations) to examine differences between groups.

Exploratory outcomes:

- 1) Differences in ISI score by engagement. We will conduct sub-analyses of change in ISI between high engagers (based on frequency of skill utilization) and low engagers (separated by median value).
- 2) Differences in ISI score by participant satisfaction. Participant satisfaction will be graded on a Likert scale, as well as whether participants would recommend the sleep program to friends or family.
- 3) We will also explore differences in fatigue and depression (common co-occurring symptoms) as measured on the PROMIS 29, by arm.

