**Objectives**

OBJECTIVES
Primary
To determine the impact of the voice-activated smart speaker CBT-I components on insomnia symptoms among breast cancer survivors using a randomized clinical trial.
Secondary
To determine differences in specific CSD metrics by intervention arm.
Tertiary/Exploratory
To determine whether there are differences in ISI change by frequency of engagement or satisfaction with the intervention.

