**4.1**

OBJECTIVES	ENDPOINTS
Primary	
To determine the impact of the voice-activated smart speaker CBT-I components on insomnia symptoms among breast cancer survivors using a randomized clinical trial.	We will collect data on the Insomnia Severity Index (ISI) total score pre- and post-intervention as our primary outcome. The ISI is a seven-item questionnaire with response categories from 0-4 (total score 0-28) asking about sleep patterns and specifically characterizing insomnia over the two weeks prior. The ISI defines 'no clinically significant' insomnia as a score of 0-7, 'sub-threshold' insomnia as a score of 8-14, 'moderate severity clinical' insomnia a scores of 15-21, and 'severe clinical' insomnia as a score of 22-28. Our clinically relevant target for success is to achieve sub-threshold or better scores ( $\leq 14$ ) among >80% of the intervention participants.
Secondary	
To determine differences in specific CSD metrics by intervention arm.	CSD Metrics: sleep efficiency, wake after sleep onset, sleep onset latency, total sleep time and sleep quality.
Tertiary/Exploratory	
To determine whether there are differences in ISI change by frequency of engagement or satisfaction with the intervention.	Among the intervention group we will also examine frequency of participant engagement and the system usability scale (SUS), including participant satisfaction with the program, and whether these factors affect ISI change.

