## PROTOCOL TITLE: Testing mHealth Delivery of Cognitive Behavioral Therapy for Insomnia to Breast Cancer Survivors

**Randomization.** After screening for eligibility, participants will complete informed consent. Our biostatistics consultant will provide randomization assignments in a 1:1 allocation ratio using a block randomized design with random block sizes between 4-6.

During the study the Sleep Helper program will collect sleep diary data via voice in an ongoing manner. At the completion of the six-week intervention individuals will complete forms via a personalized REDCap link. If individuals complete >50% of the items on a scale mean substitution of missing values with respondent's average response on remaining scale items will be used.

This study will use Amazon Alexa Echo Dots. Participants will also receive a hotspot and a smartphone, so that they do not have to rely on personal wifi (thus further protecting their identity). These devices will be supplied to participants at no cost. We do not foresee any significant risk in using this device. This device is exempt from IDE regulation as it is in commercial distribution and is used in accordance with the indications in labeling.

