**Data collection.** Baseline data before randomization will be collected from all participants using REDCap. We will have a separate link to a password protected recruitment document (with name and contact information) where unique study IDs will be assigned, thus further protecting the identity of participants. In the de-identified REDCap forms we will collect information on basic demographics (e.g. age, race/ethnicity, body mass index, education, marital status), medical history (e.g. comorbidities, time since treatment), and lifestyle habits (e.g. physical activity, alcohol consumption) as well as our primary outcome of the Insomnia Severity Index (ISI). Before randomization and upon completion of the intervention and control, participants will be administered surveys of relevant questions from the CSD through REDCap. We will collect basic sleep information including time getting into bed, time attempting to go sleep, time awake during the night, time awake in the morning, time getting out of bed, number of awakenings, and quality of sleep. We will also collect information on the PROMIS 29-item scale to see how co-occurring symptoms such as fatigue and anxiety are distributed by group. Additional information to be collected includes a morning/eveningness questionnaire to assess chronotype and participant expectations and motivations. All data will be self-reported.

Ongoing data collected through the Alexa app includes basic sleep information including time getting into bed, time attempting to go sleep, time awake during the night, time awake in the morning, time getting out of bed, number of awakenings, and quality of sleep. The ongoing data collected is used to inform treatment recommendations, but is not considered in the primary or secondary outcome analyses, which are based on the ISI and CSD.

Upon completion of the program, participants in the intervention arm will complete a system usability scale as well as a set of open-ended feedback questions after completion of the other REDCap forms.

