### **14.0 Withdrawal of Subjects\***

#### **DISCONTINUATION OF STUDY INTERVENTION/EXPERIMENTAL MANIPULATION**

When a subject discontinues using the Sleep Helper skill but does not withdraw from the study, remaining study procedures will be completed as indicated by the study protocol. The investigator or qualified designee will determine if any change in participant management is needed.

The data to be collected at the time of study intervention discontinuation will include the following:

- The reason(s) for discontinuing the participant from the intervention, and methods for determining the need to discontinue
- The participant will be asked to complete the post-interventions assessments, even though not participating in the intervention

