## 17.0 Data Management\* and Confidentiality

### ○ STATISTICAL HYPOTHESES

- Primary Endpoint(s): Insomnia Severity Index

We hypothesize that, compared to participants who receive a control intervention, participants who receive Cognitive Behavioral Therapy for Insomnia via the Sleep Helper skill will have lower ISI scores at the end of the six-week intervention. Alternatively, our null hypothesis is that there will be no difference in the ISI score between groups at the end of the six-week intervention. Thus our primary efficacy outcome is based on the continuous ISI scale. We plan to also conduct a categorical analysis: we further hypothesize that a greater percentage of those in the intervention arm will have a clinically significant reduction in ISI score to <14, or sub-threshold insomnia, than in the control arm.

- Secondary Endpoint(s): CSD Metrics

Our statistical objective is exploratory in that we are interested in whether we are seeing changes in metrics of the CSD. We will evaluate the following CSD metrics: sleep efficiency, wake after sleep onset, sleep onset latency, total sleep time and sleep quality.

- Exploratory Endpoint(s): We will analyze whether we see differences in ISI change by level of engagement and satisfaction with the intervention.

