### ○ SAMPLE SIZE DETERMINATION

## PROTOCOL TITLE: Testing mHealth Delivery of Cognitive Behavioral Therapy for Insomnia to Breast Cancer Survivors

We based our power calculations on the null hypothesis of no significant mean adjusted difference between groups post-intervention on a continuous total ISI score, after controlling for baseline score using Analysis of Covariance (ANCOVA). A systematic review and meta-analysis published in 2016 showed a large effect size of  $d=0.77$  (95% CI 0.60-0.93) at post-treatment across seven randomized controlled trials {Johnson, 2016 #740}. A recent study of internet-based CBT-I among breast cancer survivors found an effect size of 1.17 where the outcome was the ISI {Zachariae, 2018 #69}.

We used Proc GLMPOWER in SAS Version 9.4 to calculate a series of required sample sizes with covariate-outcome correlations (0.5-0.8) with a desired power of 80% to detect effect sizes between .50 and .80 (medium to large). N values included in the table are for total sample size. Alpha was set at .05 (2-sided test).

Effect size	Correlation 0.5	Correlation 0.6	Correlation 0.7
0.5	N=98	N=84	N=68
0.65	N=58	N=50	N=40
0.8	N=40	N=34	N=28

Estimating a conservative effect size (based on prior literature) of 0.65 and a pre-post correlation of 0.5, we would need N=58 participants, or n=29 per arm. We will aim to recruit N=76 total (n=38 per arm) to allow for drop out of up to 30%.

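### The secondary analysis names only means and SDs for the five sleep-diary metrics and does not state whether or how their baseline values are used

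*Combined protocol and SAP*

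**What the plan says.** - **Objective and endpoint.** Section 2.0 gives the secondary objective as "To determine differences in specific CSD metrics by intervention arm". Section 4.1 lists the endpoint as "CSD Metrics: sleep efficiency, wake after sleep onset, sleep onset latency, total sleep time and sleep quality".
- **Data.** Section 6.0, under Data collection: "Before randomization and upon completion of the intervention and control, participants will be administered surveys of relevant questions from the CSD through REDCap". Each metric can therefore have a baseline and a post value in both arms.
- **Method.** Section 17.0, Analysis of the Secondary Endpoint(s), says that differences between arms will be calculated for the five metrics, then gives one method: "We will calculate descriptive statistics (means and standard deviations) to examine differences between groups". No model, covariate or interval is named.
- **Status.** Section 17.0, Statistical Hypotheses: "Our statistical objective is exploratory in that we are interested in whether we are seeing changes in metrics of the CSD".
- **Contrast with the ISI.** Analysis of the Primary Endpoint(s) specifies ANCOVA controlling for baseline ISI, and logistic regression controlling for baseline ISI for the categorical analysis.
- **Missing data.** Populations for Analyses promises intent to treat for primary and secondary analyses. Multiple imputation is planned for the primary analysis only, if completers and dropouts differ importantly at baseline or if loss exceeds 10%. Section 6.0 covers missing items within a scale ("If individuals complete >50% of the items on a scale mean substitution of missing values"). Section 14.0 covers women who stop using the program: "The participant will be asked to complete the post-interventions assessments, even though not participating in the intervention".

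**The concern.** Post means, change scores and a baseline-adjusted model would all be consistent with the secondary-endpoint text. They estimate the same randomised effect with different precision, and the choice could be made after the results are seen. The Statistical Hypotheses text speaks of changes in the CSD, but the analysis text does not turn that into a method. The trial is sized on the ISI alone, so the CSD differences will be imprecise, and the baseline values that might sharpen them are already being collected.

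The smaller, second issue is missing forms. Neither the item-substitution rule nor the request to women who stop the program says what happens when no post-intervention CSD form exists. Means of the returned forms would describe completers, which falls short of the intent-to-treat secondary analysis the plan promises.

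**Working it through.** **Inputs from the documents.** 1:1 allocation; two-sided alpha 0.05; 58 women required (29 per arm) for ISI effect size 0.65, pre-post correlation 0.5 and 80% power; 76 recruited (38 per arm); dropout of up to 30%.

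**Assumption.** No CSD baseline-to-post correlation r is given, so r = 0.1 to 0.7 is assumed. Section 6.0 does not say how many nights the CSD survey covers, so a low r cannot be ruled out. All widths are in units of the post-value SD.

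**The plan's own figure.** ANCOVA power from the noncentral F distribution, with residual SD √(1 − 0.5²) and N − 3 degrees of freedom, gives 80.2% at N=58. All nine cells of the sample-size table reproduce. The documents state no figure for the CSD.

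**Half-widths of the 95% interval at N=58**

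- Standard-error factor: √(1/29 + 1/29) = 0.2626.
- Unadjusted post values: t(0.975, 56) × 0.2626 = 2.0032 × 0.2626 = 0.526.
- ANCOVA: t(0.975, 55) × 0.2626 × √(1 − r²) = 2.0040 × 0.2626 × √(1 − r²).
- Change scores, if baseline and post SDs are equal: 0.526 × √(2(1 − r)).

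| r | ANCOVA | Narrower than post values by | Change score |
|---|---|---|---|
| 0.1 | 0.524 | 0.5% | 0.706 |
| 0.2 | 0.516 | 2.0% | 0.665 |
| 0.3 | 0.502 | 4.6% | 0.622 |
| 0.5 | 0.456 | 13.4% | 0.526 |
| 0.7 | 0.376 | 28.6% | 0.407 |

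With equal SDs, change scores are less precise than post values when r is below 0.5 and more precise above it. With unequal SDs the crossover is at r = SD(baseline) / (2 × SD(post)): 0.4 if the baseline SD is 0.8 times the post SD, and 0.625 if it is 1.25 times. ANCOVA is the narrowest of the three at every r in the table.

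**Other sample sizes.** At N=53 (76 × 0.70 = 53.2; arms of 26 and 27) the half-width is 0.552 unadjusted, and 0.526, 0.478 and 0.394 with ANCOVA at r = 0.3, 0.5 and 0.7. At N=76 it is 0.457 unadjusted, and 0.436, 0.396 and 0.327 with ANCOVA. The percentage gains are nearly the same as at N=58.

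**Missing forms.** 76 × 0.10 = 7.6, so losing 8 or more women triggers imputation of the ISI. 76 × 0.30 = 22.8, so the dropout allowance is about 23 women. Nothing states how the same women's missing CSD would be handled.

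**The case against.** The strongest reply is that a descriptive CSD analysis is deliberate. The objective is called exploratory, the method is descriptive, and the sample size rests on the ISI; these fit together. That stands to a large extent. No confirmatory CSD test is missing, and nothing here touches the primary conclusion. But an exploratory label limits what may be claimed. It does not settle which difference is reported or argue against using baseline data already in hand.

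It may also be said that the general two-tailed 0.05 rule covers the CSD. It sets a level but names no CSD model or covariate.

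A further reply is that the gain is assumed and may be near zero. That also stands: at r = 0.1 it is 0.5%.

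Two stronger readings are tempting. A reader might infer that the plan discards the baseline CSD values. The documents do not support this: the analysis text is silent rather than exclusive, and the mention of changes in the Statistical Hypotheses text suggests that baseline may be used at least descriptively. A reader might also infer that the planned comparison is biased. Lack of baseline adjustment does not bias a comparison of randomised arms; it costs precision only.

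**Conclusion.** The gap is real but modest: the plan does not state whether or how baseline CSD enters the secondary comparison. Under the assumed r of 0.1 to 0.7, the precision forgone by comparing post values alone is between 0.5% and 28.6% of the interval half-width at N=58. The gap itself is certain; its size depends on a correlation the documents do not give, and the change-score figures also need equal SDs at the two times. Leaving the choice open matters even at low r: with r = 0.3 and equal SDs, change scores would widen the interval by about 18% over post values (0.622 / 0.526 = 1.18).

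The missing-form point is a separate inconsistency between the intent-to-treat promise for secondary analyses and an imputation rule limited to the primary. Taken together, priority is optional to low: worth correcting because it is cheap, not because the trial's main result depends on it.

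**What to change.** In Analysis of the Secondary Endpoint(s):

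1. For each of the five metrics, fit an ANCOVA of the post value on arm and that metric's own baseline, and report the adjusted mean difference with a 95% confidence interval. (No endpoint in the plan, including the ISI, is given an interval.)
2. Keep the means and SDs as description, saying which time points they summarise. Keep the exploratory label and make no confirmatory claim across the five metrics.
3. Name in advance a transformation, or a robust or bootstrap interval, for any of the five metrics whose residual checks fail. Include sleep quality, whose scale the documents do not give.
4. For missing post-intervention CSD, apply multiple imputation under the same triggers as the ISI, with arm, baseline CSD and predictors of dropout in the imputation model. Describe it as a missing-at-random analysis; the not-missing-at-random wording in the primary section should not be carried over, because imputing from observed predictors assumes missing at random.

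The cost is SAP wording, five models with residual checks, and an imputation step if triggered. No new forms, visits or participants are needed. The text should be settled before outcomes are examined by arm.

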**2.2**

We hypothesize that our program will reduce insomnia measured by the insomnia severity index (ISI) to sub-clinical threshold levels overall (intent to treat analysis). We also will test whether those with higher adherence report greater improvement in insomnia symptoms.

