### ○ POPULATIONS FOR ANALYSES

For our primary and secondary analyses we will be using intent to treat. In tertiary analyses we will conduct analyses by adherence (median frequency of engagement).

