#### Analysis of the Primary Endpoint(s)

The ISI is a seven-item questionnaire with response categories from 0-4 (total score 0-28) asking about sleep patterns and specifically characterizing insomnia over the two weeks prior. Our primary analysis endpoint will use this continuous ISI score.

We will test for assumptions of linearity of regression, homogeneity of error variances, independence of error terms, normality of error terms, and homogeneity of regression slopes. We will use analyses of covariance (ANCOVA) to compare the two groups, which controls for baseline ISI values. We will analyze the treatment effect using the intent-to-treat principle. Descriptive statistics will examine differences in baseline variables between completers and dropouts. If important differences are observed (suggesting the data are missing under a “Not Missing at Random” mechanism) or the loss to follow-up rate exceeds 10%, the primary analysis will be tested through multiple imputation of the ANCOVA model, where potential predictors of dropout will be included in the imputation model, e.g., response to a baseline question asking about the degree of motivation of the participants to stay in the study.

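### The exploratory engagement analysis splits usage at the median and compares ISI change with no stated baseline term, which wastes information and leaves one avoidable route to a spurious association

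*Combined protocol and SAP*

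**What the plan says.** Section 2.2 sets out the hypothesis: "We also will test whether those with higher adherence report greater improvement in insomnia symptoms". The endpoint table in Section 4.1 places the analysis in one arm: "Among the intervention group we will also examine frequency of participant engagement and the system usability scale (SUS". Under Populations for Analyses the cut-point and rank are given: "In tertiary analyses we will conduct analyses by adherence (median frequency of engagement". The first exploratory outcome, under Analysis of the Secondary Endpoint(s), gives the method: "We will conduct sub-analyses of change in ISI between high engagers (based on frequency of skill utilization) and low engagers (separated by median value". No test, covariate or continuous version of engagement is stated.

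Baseline adjustment is stated elsewhere. For the primary endpoint the plan says "We will use analyses of covariance (ANCOVA) to compare the two groups, which controls for baseline ISI values", and the logistic regression for sub-threshold ISI also controls for baseline score. Both are comparisons between arms.

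The second exploratory outcome, satisfaction, is described differently and has no median split: "Participant satisfaction will be graded on a Likert scale, as well as whether participants would recommend the sleep program to friends or family".

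**The concern.** Frequency of use is a numeric measure. Cutting it at the median treats a woman just above the middle as identical to the heaviest user. With 38 women randomised to the arm, or about 27 if 30% drop out (38 × 0.70 = 26.6), little information can be spared.

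The second problem is the outcome scale. Change in ISI is negatively correlated with baseline ISI: a woman who enters at the minimum eligible score of 8 can improve by at most 8 points, while one who enters at 25 can improve by 25. If worse sleepers use the program more, heavy users will show larger falls even if use does nothing. If they use it less, a real association can be hidden.

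At stake is how the adherence hypothesis in Section 2.2 is read. Better adherence is part of the protocol's rationale for the smart speaker, so a positive finding is likely to be taken as support for the product.

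**Working it through.** **Inputs from the protocol (Sample Size Determination).** Planning pre-post correlation r = 0.5, range considered 0.5 to 0.8; 29 evaluable and 38 recruited per arm; dropout up to 30%. "Alpha was set at .05 (2-sided test".

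**Not in the documents, so assumed.** The distribution of engagement, its correlation c with baseline ISI, the SDs of baseline and post-intervention ISI, and the size of any engagement slope.

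**1. The plan's own figure.** No figure is given for the engagement analysis. The nearest is N = 58 for the primary ANCOVA (d = 0.65, r = 0.5, 80% power). The noncentrality is 0.65 × √58 / 2 / √(1 − 0.25) = 2.86 on 55 df, giving power of 80.2%. N = 56 gives 78.7%, so N = 58 is reproduced.

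**2. Cost of the split.** The information kept is the squared correlation between engagement and its above-median indicator. For normal engagement this is 2/π = 0.637, a loss of 36%. The loss is 25% for a uniform distribution, 19% for a U-shaped one, 52% for an exponential and 73% for a lognormal with sigma 1.

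**3. Cost of unadjusted change.** With equal SDs (set to 1) and engagement unrelated to baseline, residual variance is 1 − r² after baseline adjustment and 2(1 − r) for change. The information kept is (1 − r²) / [2(1 − r)] = (1 + r)/2.

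| r | (1 + r)/2 | × 0.637 | Combined loss |
|---|---|---|---|
| 0.5 | 0.75 | 0.477 | 52% |
| 0.6 | 0.80 | 0.509 | 49% |
| 0.7 | 0.85 | 0.541 | 46% |
| 0.8 | 0.90 | 0.573 | 43% |

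At r = 0.5 the combined loss is 39% for U-shaped engagement, 44% for uniform, 64% for exponential and 80% for lognormal.

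**4. Unequal SDs.** Let k be the baseline SD divided by the post-intervention SD. At r = 0.5 the variance of change is 1 + k² − k, and its correlation with baseline is (0.5 − k)/√(1 + k² − k).

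| k | Variance of change | Information kept: 0.637 × 0.75 / variance | Loss | Correlation of change with baseline |
|---|---|---|---|---|
| 1.0 | 1.00 | 0.477 | 52% | −0.50 |
| 0.9 | 0.91 | 0.525 | 47.5% | −0.42 |
| 0.8 | 0.84 | 0.568 | 43% | −0.33 |
| 0.7 | 0.79 | 0.604 | 40% | −0.23 |

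**5. Power (simulation; r = 0.5, k = 1, normal engagement, assumed slope 0.4 SD of ISI per SD of engagement).** At n = 38, median split on unadjusted change gives 44%, against 75% for continuous engagement with baseline ISI. At n = 29 the figures are about 36% and 63%.

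**6. False positives (simulation; no engagement effect given baseline, r = 0.5, k = 1).** The expected high-minus-low difference in change is −(1 − 0.5) × c × 2√(2/π) = −0.80c SD.

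| c | Expected difference (SD) | n = 29 | n = 38 |
|---|---|---|---|
| 0 | 0 | 5% | 5% |
| 0.2 | −0.16 | 7% | 7% |
| 0.3 | −0.24 | 9% | 11% |
| 0.5 | −0.40 | 18% | 22% |

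With baseline ISI in the model the rate is about 5% in every row. At n = 38 and c = 0.5, unadjusted change gives about 17%, 12% and 8% for k = 0.9, 0.8 and 0.7; at c = 0.3 it gives about 9%, 7% and 6%.

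**The case against.** The strongest objection is that the plan does not say the change score will be unadjusted. It names no model, and change in ISI can be analysed with baseline as a covariate, which gives the same group estimate as ANCOVA on the post score. This stands as a limit: the lack of adjustment is inferred from silence. The inference is reasonable because the plan names baseline control for both between-arm models and not here. The median split is not inferred; it is stated twice.

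A reader might conclude that the planned analysis throws away over half the information. The documents do not support that as a general statement. It needs the split and unadjusted change together, r at the bottom of the protocol's range, roughly normal or right-skewed engagement, and equal SDs. Entry requires ISI of at least 8, which truncates baseline scores only, so a smaller baseline SD is plausible.

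A reader might also infer that a false engagement effect is likely. That depends on a correlation between engagement and baseline ISI that the documents do not give; at zero there is no inflation.

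Finally, the analysis is labelled exploratory and no power is claimed for it. That limits the consequence but is not a reason to keep the weaker method.

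**Conclusion.** The point holds in a limited form. The stated method has a better and nearly costless replacement. Under normal engagement the split alone costs about 36% of the information. If change is unadjusted, the total is about 43% to 52% for r from 0.8 to 0.5 with equal SDs, and 40% to 47.5% at r = 0.5 if the baseline SD is 0.7 to 0.9 of the post-intervention SD. The false-positive rate runs from 5% to about 22% over assumed engagement-baseline correlations of 0 to 0.5 at r = 0.5 with equal SDs, and is lower if the baseline SD is smaller.

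Three limits apply. The median-split criticism does not extend to the satisfaction outcome. Baseline adjustment closes only one route of confounding: engagement is not randomised, and motivation, for example, may drive both use and improvement. The primary comparison is untouched, so the effect is on how the engagement finding is interpreted.

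**What to change.** Replace the first exploratory outcome with wording such as: within the intervention arm, post-intervention ISI will be regressed on baseline ISI and engagement frequency as a continuous variable, on a scale fixed before the data are seen (for example rank or log); the slope will be reported with a 95% CI as a non-causal association. Keep the high and low engager groups as a descriptive table, and bring Populations for Analyses into line.

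The cost is a sentence or two. ISI is already collected at both times, and the existing analysis already needs usage frequency. There is a small downside: a slope assumes a shape, and with about 27 to 38 women a few extreme users can move it. Fixing the scale in advance and showing the descriptive table alongside limits that risk.
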